Given the rapidly developing nature of the COVID pandemic and the short timeline for submitting the initial NIH grant proposal, we have subsequently made some changes to the design of the study that will improve the quality and rigor of the science and allow for more robust comparisons. The NIH allows for changes in design that improve the quality and rigor of the science. Notably, we have added a control group (n=15) that will receive a tablet with standard guidelines for exercise following COVID-19 infection and hospitalization, the Platform (for testing only) and a Fitbit activity monitor, but not any formal tele-rehabilitation. To collect safety data and encourage retention, a research assistant will contact control participants 1x/week over the course of the intervention (12 weeks). The intervention group (n=30) will receive care as described herein. Therefore, the total projected sample size for this study will be 45 participants. Including a formal control group in addition to the intervention group will allow for more robust evaluation of the value of tele-rehabilitation sessions combined with biobehavioral interventions. We will still be able to compare both the intervention and control groups described to a no-treatment sample that is followed as part of COMIRB 20-0703. We therefore believe the proposed changes are justified to improve the quality of the science and the comparisons/conclusions we will be able to make from these data.

Research Design and Methods

For this rehabilitation pilot, individuals from a separate hospital follow-up study (COMIRB 20-0703) who are 35 years of age and older and speak English will be randomly approached regarding potential participation. Participants will also be recruited through treatment relationships with [name], [name], and [name] (Co-Investigators). Participants will also be recruited via HIPAA A and COMIRB approved flyers in Colorado. Individuals who consent to participate will be randomly allocated to the intervention or control group in a 2:1 ratio; randomization will be stratified based on age (<55 and ≥55), length of mechanical ventilation (<5 days, ≥ 5 days), and gender. The **App-Facilitated Tele-Rehabilitation (AFTER)** program involves tele-rehabilitation delivered in individual formats with biobehavioral interventions to augment adherence and recovery. Outcome assessors will be blinded to group allocation within the AFTER program.

A. Outcome Measure(s):

Data Collection and Outcomes.

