Outcomes, unless specified otherwise, will be collected at baseline, week 6 (primary endpoint), week 12, and week 26. Baseline testing will occur following the pre-session to set up the Platform and prior to the Physical Therapy Evaluation (session 1). The primary functional outcome for Hypothesis B (30" chair stand test) will be collected through the Platform (more details below). Each test session will include the standardized procedures described in the next sections. Importantly, all test sessions will occur in the participant's home and when possible, be facilitated via the Platform and verified concurrently by a trained outcomes assessor who oversees the testing remotely.

Feasibility (Hypothesis A) will be measured by program adherence, defined as the number of sessions attended divided by the total number of prescribed sessions (n=12). Individuals will be considered adherent if they attend at least 75% (9 visits) of the total sessions. Secondary adherence will be measured by the number of days the HEP is completed divided by the total number of prescribed sessions (n=60 [5x/12 weeks]), with adherence defined by completion of ≥ 75% (45 sessions) of prescribed sessions. System Usability Scale (SUS) will be collected at program end only. The SUS is a 10-item survey that uses a 5-point Likert scale (Strongly disagree (1) to Strongly agree (5)). Scores range from 0 to 100 and higher scores indicate better usability. It is a valid scale and is frequently used by the Platform to assess its usability. Safety will also be measured as a marker of feasibility. Safety events will be categorized and counted; safety events will be collected during each session and through the diary feature on the Platform. Additionally, falls will be graded using the Falls-Grading Scale.⁸³ The scale ranges from 1 to 4; a grade of 1 is defined as a near fall, grade 2 is a fall that does not receive medical attention, grade 3 is a fall that requires medical attention but no hospital admission, and grade 4 is a fall resulting in hospital admission. All the aforementioned outcomes will be collected in the intervention group, and only safety will be collected in the control group.

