Initial efficacy for change in physical function will be measured by the 30" Chair Stand Test (Hypothesis B primary outcome). The 30" Chair Stand Test requires only a standard height chair (approximately 45cm) and can be visualized on video. The test requires the participant to stand up and sit down as many times as possible in 30 seconds. To facilitate accuracy of the test over video, the participant will be instructed to count out loud during the test each time he/she stands. Further, the test will also be facilitated by the Platform. The 30" Chair Stand Test is responsive to change. Initial efficacy for behavior change will be assessed by Average Daily Step Count, PROMIS Short Form (SF) v1.0 General Self-Efficacy 4a, and PROMIS Short Form (SF) v1.0 Self-Efficacy for Managing Chronic Conditions. Average Daily Step Count (per week)

will be collected via Fitbit. The PROMIS SF v1.0 General Self-Efficacy 4a was developed from the NIH self-efficacy scale, and the short form consists of 4 items rated on a 5-point Likert scale [I am not at all confident (1) to I am very confident (5)].⁸⁴ The PROMIS SF v1.0 Self-Efficacy for Managing Chronic Conditions will also be collected since items on this scale are more specific to managing symptoms during various tasks. The short form is an 8-item scale rated on a 5-point Likert scale which is identical to the General Self-Efficacy scale. It has been validated in individuals with chronic neurological and general medical conditions.⁸⁵ For both PROMIS measures, a higher score is indicative of higher levels of self-efficacy. Additional outcomes for Hypothesis B include 4-stage balance test, Timed Up-and-Go test, MRC dyspnea, and activities-specific balance confidence (ABC) scale to identify and monitor fall risk. The PROMIS Scale v1.2 Global Health will be used to measure quality of life; a higher score is indicative of better quality of life. The 3-Item Loneliness scale will be used to assess loneliness. The Patient Health Questionnaire 8 (PHQ8) will be used to measure depression; a higher score indicates increased severity of depressive symptoms. All the aforementioned outcomes will be collected in both groups.

The following is specific to data collected through the Platform:

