3) 4-stage balance test: The 4-stage balance test measures static balance in 4 different positions (narrow base of support, semi-tandem, tandem, and single-leg). The test is facilitated by the Platform; it requires participants to hold each position for up to 10 seconds. If a participant is unable to hold a position for 10 seconds, the next hardest position is not performed (e.g. if participant unable to hold semi-tandem for 10 seconds, then the test stops, and tandem and single-leg stance are not assessed). The 4-stage balance test is indicative of fall risk.

4) MRC Dyspnea. Interviewer-administered or self-report assessment of the perception of difficulty breathing during five different tasks. Participants respond either yes or no to each task.

5) Montreal Cognitive Assessment (MoCA)-BLIND. The MoCA-BLIND is an adapted version of the original MoCA, a rapid screening instrument for mild cognitive dysfunction. The MoCA-BLIND assesses different cognitive domains: attention, concentration, memory, language, conceptual thinking, calculations, and orientation. The MoCA-BLIND has removed assessments

requiring vision, thus can be completed using telehealth or telephone assessments. It will be collected only at baseline.

Participants will complete online questionnaires including: 1) Assessment of pre-hospitalization and post-hospitalization frailty. Participants will estimate function using the Clinical Frail Scale, an easy to interpret estimate of function that has been validated in several populations. The participant will select perceived level of function prior to and following admission ranging from very active to bedridden/terminal. Additional questionnaires are described above for Hypotheses A and B and will be collected either through the Platform or online via REDCap survey.

Characteristics of patients and of the hospitalization are collected from the medical record in all hospitalized COVID-19 patients (COMIRB protocol 20-0690), including duration of hospitalization, need for and duration of mechanical ventilation, comorbidities, medications, demographics, and zip code among others. Post-hospitalization data is also collected, including readmission, need for/duration of supplemental oxygen, receipt of rehabilitation care, imaging, and laboratory results. Electronic medical records for participants not hospitalized in the UCH system will be requested using a HIPAA A form.

The AFTER Program Procedures (Intervention Group).

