Participants will be screened for safety and high fall risk upon entry into the program, but the **design of the intervention is to target even the most medically deconditioned participants and tailor the program to address any safety concerns** (e.g., sitting exercises with progression to standing as able). Prior to starting the 6-week program, enrolled participants will receive step-by-step instructions to trial the Platform; a research assistant will help the participant troubleshoot technical issues. The treating therapist will modify the set-up as needed during session 1 and throughout the program. The therapist will monitor and assess the patient, progress the rehabilitation program, and track adherence through the Platform and videoconferencing. Validated physical function measures and surveys will also be collected through the Platform at testing timepoints (baseline, week 6, week 12, and week -26), and may be collected up to every 2 weeks during both phases of the program.

Some telerehabilitation sessions will be audio and/or video recorded to verify interventionist fidelity. Participants will be given the option to allow or to disallow any recordings.

D. Description, Risks and Justification of Procedures and Data Collection Tools:

Exercise:

We recognize there may be an increased risk for falls with greater exposure to physical activity and reduced functional capacity due to recent hospitalization. However, the increase in balance, confidence, and mobility gained through this rehabilitation program may also decrease fall risk over the long term.

Confidentiality and privacy:

The use of questionnaires and collection of personal medical information poses a risk to confidentiality and privacy (see Protection Against Risk below). Additionally, subjects may experience distress when answering questions related to their recent hospitalization.

Adequacy of Protection Against Risks

Protection Against Risk:

The inclusion/exclusion criteria are designed to assure that the sample is as representative as possible of the population of patients who are hospitalized for COVID-19 and allows the participants most likely to benefit from the rehabilitation intervention while excluding women who are known to be pregnant and who would therefore have expected variability beyond that of other patients.

Rehabilitation and Exercise:

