Intervention will be carefully monitored and progressed on an individual basis by a licensed physical therapist. Education on muscle soreness, shortness of breath, and fall risk reduction

will occur before any intervention is initiated. Education will also include signs of distress that should be communicated to the study team (e.g., dizziness, light headedness, symptoms of myocardial infarction). Participants who are identified to be at risk for falls will initially perform exercises seated or while holding onto a sturdy surface. When training is performed in standing or walking (e.g., conditions with a potential risk for falling), safeguards will be taken to ensure a sturdy surface is nearby for steadying should a loss of balance occur. For the purpose of safety monitoring, we will consider any fall, defined as “inadvertently coming to rest on the ground, floor or other lower level, excluding intentional change in position,” (World Health Organization) as unrelated, possibly, probably, or definitely related to study procedures. Baseline fall risk will be evaluated using the Platform (ABC scale questionnaire and the 4 Stage Balance Test) to inform each individual rehabilitation plan. Exercise will then be tailored to address any safety concerns (e.g., sitting exercises with progression to standing as able, additional balance-focused exercises). Occurrence, circumstances around, and injury associated with any fall will be recorded via the Platform’s health diary feature and a red flag notice will display on the dashboard if a fall is recorded. The treating physical therapist will also ask about falls and other adverse events (AEs) at each session for the intervention group, and a research assistant will ask about falls and other AEs during each weekly follow-up for the control group. Due to remote nature of the AFTER program, we will institute emergency procedures to respond to any AE that occurs during individual sessions. The physical location of participants will be verified prior to each individual session in the event that emergency response is necessary (call to 911). Any reported falls occurring outside of individual sessions will be discussed at the subsequent individual session or within 24 hours if medical care is required. Fall occurrences (injurious and non-injurious) and other AEs will be reported directly to the PI. Other exercise side-effects, such as muscle pain, fatigue, shortness of breath, and minor strains during therapy will be documented and monitored by [name] and [name] in consultation with [name]. Based on the existing literature and our own clinical experience with tele-rehabilitation (VA RR&D I01RX002417), we anticipate the frequency of these side-effects to be extremely low.⁹⁵

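### No fall or adverse-event enquiry is scheduled after the week 9-10 booster (AFTER) or week 12 (controls), although testing runs to week 26, and the arms are asked on different schedules before that

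*Combined protocol and SAP*

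**What the plan says.** Hypothesis A (Hypotheses and Specific Aims) anticipates no injuries. Under Outcome Measure(s), safety is a marker of feasibility: events are to be categorized and counted, falls graded from 1 (near fall) to 4 (fall leading to admission), and safety is the one Hypothesis A outcome also collected in controls. The collection rule is that "safety events will be collected during each session and through the diary feature on the Platform". The general timing rule is: "Outcomes, unless specified otherwise, will be collected at baseline, week 6 (primary endpoint), week 12, and week 26".

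The section on protection against risk (Rehabilitation and Exercise) names who asks. In the AFTER arm the question falls to the therapist, whenever a treatment session is held. The control arm has a separate rule: "a research assistant will ask about falls and other AEs during each weekly follow-up for the control group". The paragraph introducing the control group limits those weekly contacts to 12 weeks. It also gives controls the Platform for testing purposes only.

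Under AFTER Program Procedures there are 12 sessions, the last being a booster in week 9 or 10. Further therapist contact in weeks 7-12 occurs only if home-exercise adherence falls below 75%. The health diary accepts hospitalizations, injuries and falls, but entry is optional self-report. Study Design and Research Methods adds record data: "Post-hospitalization data is also collected, including readmission".

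**The concern.** Both routes of active enquiry end long before the last test point, and they end at different times. The assessments listed for weeks 6, 12 and 26 include fall-risk measures (for example the "activities-specific balance confidence (ABC) scale to identify and monitor fall risk") but no question on whether the participant has fallen, been injured or been admitted.

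Two things are at stake. First, a finding of few or no injuries is weak support for Hypothesis A over any period in which nobody asked. Second, the two arms are asked by different people on different schedules, so a difference or similarity in counts cannot be separated from a difference in ascertainment. The contrast is sharpest in weeks 7-12. AFTER participants are then responsible for progressing their own exercises and have one scheduled enquiry, while controls are still called every week.

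**Working it through.** **Inputs.** AFTER n = 30, controls n = 15 (control-group paragraph). Session schedule: 3 in week 1, 2 per week in weeks 2-4, 1 per week in weeks 5-6, 1 booster in week 9 or 10 (AFTER Program Procedures). Control calls: weekly for 12 weeks. Last test point: week 26.

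**The plan's own figure.** 3 + 2×3 + 1×2 + 1 = 12 sessions, which matches the stated 12. The booster is therefore the last scheduled occasion on which an AFTER participant is asked.

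**Weeks without scheduled enquiry.** Weeks up to the booster are counted as covered, since the therapist can ask about the time since the previous session. This is generous to the plan.
- AFTER: 26 − 10 = 16 to 26 − 9 = 17 weeks (16/26 = 62% to 17/26 = 65%).
- Controls: 26 − 12 = 14 weeks (14/26 = 54%).

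**Person-weeks, assuming full follow-up.**
- Total: 45 × 26 = 1,170.
- Not covered, booster in week 10: 30×16 + 15×14 = 480 + 210 = 690 (59%).
- Not covered, booster in week 9: 30×17 + 15×14 = 510 + 210 = 720 (62%).
- Of these, 45 × 14 = 630 (54%) fall in weeks 13-26, when neither arm has a scheduled enquiry. The other 60 to 90 are AFTER person-weeks between the booster and week 12.

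**Enquiries per participant within the 12-week program.**

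| Period | AFTER | Controls |
|---|---|---|
| Weeks 1-6 | 3 + 6 + 2 = 11 | 6 |
| Weeks 7-12 | 1 | 6 |
| Total | 12 | 12 |

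The totals agree, but the timing does not.

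**What the remaining routes can catch.** Readmission data may capture grade 4 falls. They are not shown to capture grade 3 (medical attention without admission), and they cannot capture grades 1 and 2. The diary could capture all grades, but entry is voluntary and control access is unclear. The plan also sends falls outside sessions that need no medical care to the next individual session, and none is scheduled after the booster.

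**What fuller collection could show.** The documents give no fall rates, so control faller proportions of 10% to 40% by week 26 are an assumption. For a halving of that proportion, with 15 versus 30 and a two-sided 5% test, power runs from 11.5% to 30.6% (normal approximation) or 6.2% to 23.8% (Fisher's exact test). Power of 80% would need about 936 participants in total at 10%, falling to 180 at 40%.

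**The case against.** The strongest reply is that the end of collection is inferred and not stated. The default schedule for outcomes runs to week 26, safety is listed among the outcomes, and a session could be read to include a test session. The diary has no stated end date, participants are encouraged to use it, and a recorded fall raises a flag on the dashboard. Following safety mainly during exposure is also a defensible choice for a pilot.

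Part of this stands: the plan does not forbid later collection, and some later events would reach the team. But the timing default yields where something else is specified, and the same section ties safety to sessions and the diary. It also counts sessions as the 12 prescribed ones, and the risk section gives the question to the treating therapist, not to the outcomes assessor. If week 26 was intended, no person or instrument has been assigned to ask.

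Three stronger readings are tempting, and the documents do not support them.
- A reader might infer that the plan makes a long-term fall claim that cannot be checked. The statement that gains from the program "may also decrease fall risk over the long term" is a tentative remark in the risk justification, not a hypothesis, endpoint or planned analysis. The diary and readmission data offer a partial check, and 45 participants could not settle the matter even with complete data.
- A reader might infer that late diary entries would come mainly from AFTER and make it look worse. Control access to the diary is unclear, not excluded, and the Data Analysis Plan gives only descriptive statistics for safety. The direction of any bias is unknown.
- A reader might take 630 person-weeks as the most that is missed. That is only the part in which neither arm is asked.

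**Conclusion.** The concern holds as a gap in safety ascertainment. Followed as written, the plan leaves 16-17 of 26 weeks in AFTER and 14 of 26 in controls without scheduled enquiry, or 690-720 of 1,170 person-weeks (59-62%). Within the program, the arms are asked on different schedules, six times versus once in weeks 7-12. Counts of injuries and falls for Hypothesis A will be incomplete and not comparable by arm.

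This rests on full follow-up to week 26, on reading sessions as treatment sessions, and on no contact beyond those scheduled; adherence-triggered therapist contacts would add some coverage in weeks 7-12. It is worth correcting because the plan hypothesises no injuries and undertakes to count events in both arms. It does not undermine the chair-stand comparison.

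**What to change.** Add one identical form on falls, injuries and admissions, completed by the participant in REDCap, in both arms at the existing week 6, 12 and 26 test points. Each form should cover the interval since the previous test point (6, 6 and 14 weeks) and be withheld from the blinded outcomes assessor. Base by-arm counts on this form, and show events from sessions, calls and the diary separately by source. Cross-check reported admissions against the readmission data already collected, with the same rule and a stated week-26 window in both arms. Report events descriptively by arm for weeks 0-12 and 13-26. State the safety observation window and whether controls have the diary.

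The cost is one short survey at test points that already exist, in a system already used for questionnaires. The downside is recall: over up to about 14 weeks minor events will be missed, possibly not equally by arm, since AFTER participants are coached in self-monitoring and know their allocation. The result would describe falls and would not be a test of fall reduction.

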In addition to the data regarding comorbidities and hospitalization which is collected through medical record review as part of COMIRB 20-0690 and 20-0703, data will be collected through the Platform. The Platform can track usage data, results from tests and measures, and health information. Usage data will be used to monitor and describe adherence to prescribed activities (e.g., Home exercise program, learning modules). It will also be used to collect the following outcomes: 30" Chair Stand Test, Timed Up-and-Go test, 4-stage balance test, system usability scale, activities-specific balance confidence (ABC) scale, and the PROMIS Scale v1.2 Global Health. While participants will be encouraged to use the Platform for this data collection since it is part of our feasibility outcome, alternatives will be provided for the main testing points (baseline, week 6, week 12 and week 26) to achieve complete data collection. Through the health diary feature, participants will be encouraged to log data pertaining to but not limited to medical history (medications, comorbidities), smoking status, demographics (age, gender, height, weight), and health events (e.g., hospitalization, injury, fall). This data entry is optional and completed via self-report. Any data entered into the Platform will be accessible by the research team. The participant's name is NEVER associated with the Platform in any way, and once a participant is enrolled, he/she will be assigned a login/password such as "Telerehab_P01" to indicate telerehabilitation study and participant 01; the initial account password is randomly generated through Blue Marble's webapp.

B. Description of Population to be Enrolled:

Potential participants will be recruited ideally during the first 2 to 6 weeks following hospital discharge to home, though if recruitment targets are slow, enrollment will be allowed up to 12 weeks post-discharge to home.

Inclusion Criteria:

1. Confirmed COVID-19, per diagnostic criteria (PCR testing)
2. Hospitalized for at least 24 hours
3. 35 years of age or older
4. Able to provide informed consent
5. Internet capability to access the platform
6. Community-dwelling prior to hospitalization

Exclusion Criteria:

1. Unstable medical comorbidities that would preclude participation in exercise
2. Receipt of >1 session of outpatient physical therapy

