3. Known pregnancy, as the impact on physical function, pulmonary function, and other outcomes will vary well beyond any expected effects of COVID 19
4. Not anticipating concurrent additional physical therapy services during study period (12 weeks)

Participants will be consented either face to face or via remote e-consent. Participants who consent remotely will be provided an e-consent via REDCap. The e-consent will be available to the participant prior to the consent discussion. A qualified study team member will Zoom phone/video call the potential participant. The potential participant will verify their identity. The study team member will explain the consent process and that the participant can navigate forward and backward through the consent form pages and that they may return to the form later if they want time to think about their participation. The study team member will read the consent form with the participant and will answer all questions that the participant has. The participant and the study team member will both sign and date the consent form and the participant will be able to download or email themselves a copy of the signed form.

C. Study Design and Research Methods

Participants will be recruited from COMIRB 20-0703 and via HIPAA A throughout Colorado.

Procedures will include

Virtual assessments include:

1) 30" Chair Stand Test (Primary Outcome). The 30" Chair Stand Test requires only a standard height chair (approximately 45cm) and can be visualized on video. The test requires the participant to stand up and sit down as many times as possible in 30 seconds. To facilitate accuracy of the test over video, the participant will be instructed to count out loud during the test each time he/she stands. Further, the test will also be facilitated by the Platform. The 30" Chair Stand Test is responsive to change.

2) Timed Up-and-Go (TUG) Test: The TUG test measures the time it takes for a person to rise from a chair, walk 3 meters, turn around, walk back to the chair, and sit down. Patients are asked to walk as quickly but as safely as they can.

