4. Although unlikely, Blue Marble's programmer may need to participate on the call to resolve the issue. The programmer has human subjects training.
5. The Research PT (or designee) will keep track of any and all technical issues as this is a feasibility outcome of the study.

F. Data Analysis Plan:

Sample Size: We estimate the proportion of participants at any session with technical difficulties (anticipate $\leq 20\%$), use the platform between sessions (anticipate $\geq 50\%$), and adhere to the intervention (anticipate $\geq 50\%$). Assuming these rates, a sample size of 30 and a two-sided 95% CI, provides a margin of error of 15% for technical difficulties and 18%, for platform use and adherence. We use preliminary 5-time chair rise data to estimate our effect size ($SD=8.7$) in our outcome and assume adjustment variables, including baseline measures, will explain at least 50% of the total variance (R^2). Using linear regression, we anticipate the width of our 95% confidence interval for the group coefficient to be $\pm 0.90 \times 1$ SD at week 6. We anticipate additional precision by using all longitudinal outcome data. We will also provide descriptive statistics for the change from baseline over time, for each group.

We hypothesize (B) tele-rehabilitation is associated with improved physical function in participants previously admitted to the hospital, as measured by change in the 30" Chair Stand Test at 12 weeks. Randomization will be stratified by age (<55 , ≥ 55), sex, and length of mechanical ventilation (< 5 days, ≥ 5 days). Hypothesis A: Descriptive statistics will assess feasibility (i.e., adherence, SUS score, and safety). Hypothesis B will be analyzed with group assignment (AFTER program versus control) as the primary explanatory variable; secondary analyses will be made to COMIRB 20-0703 cohort. Analyses will utilize R (<https://www.R-project.org>), SAS (Cary, NC), and GraphPad Prism (San Diego, CA). Code will be portable and reproducible with documenting libraries and raw data location, as well as code documenting cleaning.

G. Summarize Knowledge to be Gained:

The proposed study will 1) address a great and urgent need to identify predictors of multisystem recovery and long-term health in survivors of COVID-19 and 2) evaluate rehabilitative care to these individuals even, and especially, when they face post-hospitalization barriers to in-person care.

H. References:

References

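### Exclusion criterion 4 is worded the wrong way round: taken literally, it bars candidates who expect no outside physical therapy and admits only those who do

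*Combined protocol and SAP*

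**What the plan says.** Section B (Description of Population to be Enrolled) gives six inclusion criteria, none of which mentions physical therapy, followed by a four-item list headed "Exclusion Criteria". Item 1 concerns unstable comorbidities. Item 2 is "Receipt of >1 session of outpatient physical therapy". Item 3 is "Known pregnancy, as the impact on physical function, pulmonary function, and other outcomes will vary well beyond any expected effects of COVID 19". Item 4 is "Not anticipating concurrent additional physical therapy services during study period (12 weeks".

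Four other places bear on the point:

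- The account of design changes, just before Research Design and Methods, says controls receive exercise guidelines on a tablet, the Platform for testing and "a Fitbit activity monitor, but not any formal tele-rehabilitation".
- Section G gives as a purpose of the study to "evaluate rehabilitative care to these individuals even, and especially, when they face post-hospitalization barriers to in-person care".
- Section C says of the medical record: "Post-hospitalization data is also collected, including readmission, need for/duration of supplemental oxygen, receipt of rehabilitation care".
- Section F says: "Hypothesis B will be analyzed with group assignment (AFTER program versus control) as the primary explanatory variable".

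**The concern.** An exclusion list works by one convention: a candidate who meets any item is ineligible. Items 1 to 3 follow it. Item 4 is phrased as a requirement for entry but stands in the list of reasons for refusal, so its literal effect is the reverse of its likely purpose.

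This sentence decides eligibility for every candidate, so two things are at stake.

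- **If screeners applied it literally,** the trial enrolled people who already had other therapy in prospect. The feasibility results (adherence, platform use, technical difficulties, safety) would then describe that group.
- **If screeners applied the presumed intent,** every enrolled participant meets an exclusion criterion as written, and the eligibility record disagrees with the protocol.

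There is also a limited efficacy question. Allocation is randomised, so outside therapy expected in both groups does not confound the comparison. It could shrink the contrast between AFTER and control only to the extent that it helps controls more than AFTER participants.

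**Working it through.** The plan gives no figure to reproduce here. The check is one of logic and of comparison between sections.

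**Step 1: read each item under its heading.**

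| Item | Condition named | Candidate with the condition |
|---|---|---|
| 1 | Unstable comorbidities that rule out exercise | Excluded |
| 2 | More than 1 outpatient physical therapy session received | Excluded |
| 3 | Known pregnancy | Excluded |
| 4 | Does **not** expect additional physical therapy in the 12 weeks | Excluded |

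For item 4, a candidate who expects no therapy meets the exclusion and is refused. A candidate who expects therapy does not meet it and passes this item, though every other criterion still applies.

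**Step 2: combine item 4 with item 2.** Classify candidates by prior outpatient sessions (more than 1: yes or no) and by expected therapy (yes or no). This gives 2 × 2 = 4 types.

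| More than 1 prior session | Expects therapy | Item 4 as written | Item 4 with the negation removed |
|---|---|---|---|
| No | No | Excluded (item 4) | Eligible |
| No | Yes | Eligible | Excluded (item 4) |
| Yes | No | Excluded (items 2 and 4) | Excluded (item 2) |
| Yes | Yes | Excluded (item 2) | Excluded (items 2 and 4) |

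Each version admits 1 type of the 4, and not the same one: the overlap is 0. This follows directly from reversing a condition and does not measure any effect on results. It does show that the two readings select separate populations, so none of the 30 + 15 = 45 planned participants can satisfy both.

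**Step 3: compare the literal rule with the rest of the document.**

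- *Item 2.* The two items can be met together, so there is no formal contradiction. The combination is odd, though: it admits only people who have had little outpatient therapy and expect more.
- *Purpose.* Section G puts particular weight on survivors who face barriers to in-person care, and section I describes the wider value of the work in terms of patients without access to standard rehabilitation. A survivor whose barriers leave no therapy in prospect is exactly the person literal item 4 refuses.
- *Control condition.* Controls get no tele-rehabilitation from the study. A control group recruited because its members expect therapy elsewhere sits awkwardly with that, although the text does not forbid outside care.

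**Step 4: look for a correction elsewhere.** The inclusion list is silent on physical therapy, and no other section supplied for review restates the rule.

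**Step 5: ask whether the planned analysis would reveal the consequence.** Section C says receipt of rehabilitation care is collected. Section F makes group assignment the main explanatory variable and names no summary or analysis of care received outside the study.

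**The case against.** The strongest reply is that this is an obvious drafting slip with no shown consequence. The sentence reads like an inclusion criterion left in the wrong list. The background section says in-person services would be out of reach for many discharged patients, so a screener following the literal rule would have turned away much of the target population and would probably have noticed. Nothing in the document suggests misapplication. That stands, and it limits the weight of the point.

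Some of the supporting evidence is also weaker than the heading itself. The control-group text describes what the study supplies and says nothing about in-person therapy elsewhere. Section G's wording covers people without barriers too. Item 2 looks back while item 4 looks forward. These passages make the literal reading implausible as intent, but they do not contradict it. The decisive evidence is the heading and the parallel form of items 1 to 3.

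The absence of an analysis of outside therapy is a side issue. It would remain if item 4 were worded correctly, because someone who expects no therapy may still receive it, and the recorded data could be tabulated whatever section F says. It should not raise the seriousness of the wording error.

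Finally, some pages, including the consent form, were not available, so the statement that nothing corrects the rule applies only to the text supplied. None of these points removes the inversion.

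**Conclusion.** The concern holds. Item 4 is reversed relative to its heading, and the text supplied does not correct it. The fault should be fixed because it lies in an operative eligibility rule, but its reach is limited to eligibility and to the description of the enrolled population. The literal and presumed rules share 0 of 4 candidate types, so the wording bears on all 45 planned participants.

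Confidence is high on the wording. It does not extend to any effect on the trial: the document does not say how the item was applied, and it gives nothing from which an effect on the 30-second chair-stand contrast could be estimated. Sample size and precision figures are unaffected. The view that the slip reverses the intended rule is an inference from the list's structure and the stated purpose, which the sponsor must confirm.

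**What to change.** 1. The sponsor should confirm which rule was intended and reconcile item 4 with its heading, with item 2 and with the control condition. If the inferred intent is confirmed, deleting the word *Not*, or moving the sentence unchanged to the inclusion list, gives the same rule.
2. Check that screening forms and past screening decisions match the confirmed rule.
3. If the check finds anyone entered or refused on the literal wording, report them. If it finds none, say so.

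The cost is a one-line amendment and a review of screening records. Sample size, visits and schedule do not change.
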